Primary analysis of the primary efficacy endpoint at Week 24 will use a Cochran-Mantel-Haenszel (CMH) test stratified by BMI at Screening ($<25 \text{ kg/m}^2$, $\geq 25 \text{ kg/m}^2$), Week -2 A1C ($\leq 9\%$, $>9\%$) and use of CSII at Screening (Yes, No). Missing observations will be imputed as non-responders. A point estimate of treatment effect will be based on the sotagliflozin minus difference in binomial proportions. A 2-sided 95% CI will be estimated on the observed difference and will be based on normal approximation methods using a continuity correction factor. The individual components of the endpoint will be summarized separately using descriptive statistics.

Sensitivity analysis of the primary endpoint will use a single imputation method to obtain a rectangular dataset. Imputations will be based on use of the last observation carried forward (LOCF) algorithm. The stratified CMH test will be applied to this imputed dataset. The stratified CMH test will also be applied to the PP dataset as an additional sensitivity analysis.

Primary analysis of the continuous efficacy endpoints will use mixed-effects model for repeated measures (MMRM) statistics based on the restricted maximum likelihood (REML) method for estimation. The analysis model will include fixed, categorical effects of treatment, BMI at Screening ($<25 \text{ kg/m}^2$, $\geq 25 \text{ kg/m}^2$), Week -2 A1C ($\leq 9\%$, $>9\%$) and use of CSII at Screening (Yes, No), time (study week), baseline-dependent variable-by-time interaction, and a treatment-by-time interaction. An unstructured (co)variance structure will be used to model the within-patient errors. Other structures will be explored by use of Akaike's information criteria should the unstructured (co)variance structure not result in model convergence. The Kenward-Roger approximation will be used to estimate the denominator degrees of freedom. The adjusted mean change from Baseline by each study week for each treatment group will be estimated in the framework of this model, as well as the between-group differences (comparing sotagliflozin to placebo) and the 95% CIs for the adjusted mean. All post-Baseline observations collected at scheduled visits will be used in the MMRM, including

data collected after the discontinuation of study drug. An analysis of covariance (ANCOVA) will be applied where only 1 post-Baseline scheduled visit occurs; ie, the MMRM analysis omitting the time-related effects.

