6.1 Inclusion Criteria

Patients must meet **all** of the following criteria listed below to be considered eligible to participate in the study. For patients not meeting eligibility requirements, the reason for exclusion must be recorded. **Note:** Patients not eligible because of laboratory result(s) may have the laboratory test(s) repeated once during the Screening Period at the discretion of the Investigator to determine eligibility:

- 1) Patient has given written informed consent to participate in the study in accordance with local regulations
- 2) Adult patients 18 years and older with a diagnosis of T1D made at least 1 year prior to informed consent
- 3) Patients are being treated with insulin(s) or insulin analog(s)
- 4) Non-fast acting insulin dose is stable ($\pm 20\%$) for 2 weeks prior to the Screening Visit
- 5) At the Screening Visit, A1C must be between 7.0% and 11.0%, inclusive
- 6) BMI ≥ 18.5 kg/m²
- 7) Must be willing and able to perform SMBG and complete the study diary as required per protocol
- 8) Females of childbearing potential must use an adequate method of contraception to avoid pregnancy throughout the duration of the study and for 30 days after the last dose of study drug. Females of childbearing potential include any female who has experienced menarche and who has not undergone successful surgical sterilization (hysterectomy, bilateral tubal ligation, or bilateral oophorectomy) or is not postmenopausal. Postmenopause is defined as no menses for ≥ 12 months without another cause. For females with questionable menopausal history (eg, irregular menstrual periods and age >40 years) a documented serum follicle-stimulating hormone (FSH) level must be ≥ 30 mIU/mL.
- 9) Females of childbearing potential must have a negative serum or urine pregnancy test prior to the start of study drug. In the case of positive urine pregnancy testing, a negative serum sample for pregnancy testing, to confirm that the patient is not pregnant, must be obtained prior to start of study.

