2.3 Sample Size and Power

The sample size will be based on satisfying design assumptions made for the primary efficacy endpoint. The primary efficacy endpoint is a binomial proportion, a composite measure of glycemic control and safety. We have assumed that the majority of treatment effect will be observed in the glycemic control portion of the endpoint and for planning purposes, the rates of SH and DKA will be equal in both treatment groups. Little data are available to estimate the <7% A1C component of the endpoint in this patient population. Data reviewed from the LX4211.1-202 Phase 2 trial in type 2 diabetes mellitus (T2DM) and from other pertinent literature sources suggests that a difference between treatment groups of at least 0.15 may be expected for this variable. We will assume this effect size for the primary endpoint, but will perform an adjustment for the expected proportion of patients not having a DKA or SH event. A conservative assumption is made that the rates of DKA and SH are independent and their union is estimated to be ≤ 0.15 . It is expected that 0.85 of the patients will not have a DKA or a severe hypoglycemic event over the course of the study. Adjusting the 0.15 effect size estimate by this value yields a target effect size for the primary endpoint ≈ 0.12 . Since the underlying placebo rate is unknown for the composite outcome, we will assume a maximum variance construct under the alternative hypothesis for binomial proportions to estimate the sample size (ie, the mean of the pooled responses rates is 0.50). Assuming a 2-sided test with $\alpha = 0.05$ and 90% power, 380 patients are needed per treatment group to detect a difference in binomial proportions of at least 0.12 for the primary endpoint. The sample size estimate will be adjusted for dropouts in a manner to reflect that the primary analysis will be conducted in the modified Intent-to-Treat (mITT) patients. Dropouts are expected to be primarily a function of noncompliance: patients stopping early their randomized treatment, but followed to the 24-week visit. It is further assumed that the dropped (noncompliant) sotagliflozin patients will respond as the placebo patients and that there will be no drop-in patients in the placebo group. These assumptions net an adjusted effect size for detection of $0.12 \times (1-0.20) \approx 0.10$, where the dropout rate over 24 weeks is assumed to be 20%. Based on this adjusted effect size, 544 patients are required per treatment group, for a total of 1088 patients across the 2 treatment groups.

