6 STATISTICAL METHODS

6.1 General Principles

All data processing, summarization, and analyses will be performed using the Hosted SAS Environment / Version 9.3 (or later) of the SAS® (SAS Institute, Cary, NC) statistical software package.

Unless specified otherwise, data will be displayed using the following treatment group labels, in the order presented:

- Placebo
- LX4211 400 mg
- Total (if applicable)

Sotagliflozin will be referred to as “LX4211” in all data displays. LX4211 is also the term used in the remaining sections of this SAP.

All data collected will be presented in listings by treatment group, center, patient, and visit (where applicable), unless otherwise specified.

Data will be presented in summary tables by treatment group, assessment, and visit (where applicable). The category “Missing” will be presented if the number missing is greater than zero for at least 1 treatment group.

Descriptive summary statistics for continuous variables will include the number of observations (N), mean, standard deviation (SD), median, minimum, and maximum.

Descriptive summary statistics for categorical variables will include frequency counts and percentages [n (%)]. Unless stated otherwise in the table shells, the denominator for percentage calculations will be the number of patients in the pertinent analysis population.

Dates will be displayed as DDMMMYYYY.

For continuous efficacy variables that are derived as percentage change from Baseline outcomes, the applied analyses and their results will be used for descriptive purposes. Exceptions to this statement are the secondary efficacy endpoints of percent change from Baseline at Week 24 in body weight and bolus insulin dose, and the other efficacy endpoints of percent change from Baseline by study visit in body weight, bolus insulin dose, total insulin dose, and basal (or non-bolus) insulin dose, where both descriptive and inferential summaries will be provided.

Analysis and summarization of treatment group comparisons for the primary and secondary efficacy endpoints will be reported in their original measurement units and converted values to accommodate regulatory review by Food and Drug Administration (FDA) and external authorities, where appropriate.

All significance tests will be 2-sided and use a 0.05 α -level unless specified otherwise.

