6.8.1 Primary Efficacy Analysis

The primary efficacy endpoint is the proportion of patients with A1C $< 7.0\%$ at Week 24 and no episode of SH and no episode of DKA from randomization to Week 24. The analysis of this endpoint will be based upon the mITT population. The frequency and percentage of patients with A1C $< 7.0\%$ at Week 24 and no episode of SH or episode of DKA from randomization to Week 24 will be presented by treatment group. For this endpoint, only positively adjudicated SH and DKA events will be assessed over the cumulative randomized 24-week Double-blind Treatment Period. The cut-off dates for the inclusion of SH and DKA events, along with other EOSIs, are described in detail in [Section 6.9.2](#). In brief, the cut-off date is the date of the last dose of double-blind study drug for SH events and 30 days after the date of the last dose of study drug for DKA.

Analysis of the primary efficacy endpoint at Week 24 will be performed using the CMH test and 95% CLs based on normal approximation methods with a continuity correction factor, as described in [Section 6.8](#) for binary efficacy endpoints. The individual components of the endpoint will be summarized separately using descriptive methods. Each of these components will be expressed as a binomial proportion: proportion of patients with A1C $< 7.0\%$ at Week 24, proportion of patients with no episodes of DKA from randomization to Week 24, and proportion of patients with no episodes of SH from randomization to Week 24.

Bar charts displaying proportions of patients with A1C $< 7.0\%$ at Week 24 and no episode of SH or episode of DKA will be presented from randomization to Week 24 by treatment groups.

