6.8.5 Subgroup Analyses

Subgroup analyses of the efficacy variables will be performed for the different levels of Baseline characteristics and the randomization stratification factors. Of particular interest are the subgroup analyses of the primary efficacy endpoint and the first secondary efficacy endpoint (ie, change from Baseline to Week 24 in A1C) by:

- Age at diagnosis (<18 years, ≥ 18 years)
- Age at study entry (<75 years, ≥ 75 years)
- Sex (Male, Female)
- Race (American Indian or Alaska Native, Asian, Black or African American, Native Hawaiian or other Pacific Islander, White, other)
- Stratification for BMI categories ($<25 \text{ kg/m}^2$, $\geq 25 \text{ kg/m}^2$)
- Stratification for use of CSII (Yes, No)
- Stratification categories of Week -2 A1C ($\leq 9\%$, $>9\%$)
- Week -2 A1C ($<7.7\%$, $\geq 7.7\%$)
- Week -2 A1C ($\leq 8.5\%$, $>8.5\%$)
- Baseline eGFR status (≥ 45 to $<60 \text{ mL/min/1.73 m}^2$, $\geq 60 \text{ mL/min/1.73 m}^2$)

For the primary efficacy endpoint, the CMH test will be stratified by BMI at Screening ($<25 \text{ kg/m}^2$, $\geq 25 \text{ kg/m}^2$; excluded if it is a subgroup variable), Week -2 A1C ($\leq 9\%$, $>9\%$; excluded if it is a subgroup variable), and use of CSII at Screening (Yes, No; excluded if it is a subgroup variable).

For the change from Baseline to Week 24 in A1C, the MMRM model will have treatment, BMI at Screening ($<25 \text{ kg/m}^2$, $\geq 25 \text{ kg/m}^2$; excluded if it is a subgroup variable), Week -2 A1C ($\leq 9\%$, $>9\%$; excluded if it is a subgroup variable), use of CSII at Screening (Yes, No; excluded if it is a subgroup variable), time (study week), and a treatment-by-time interaction as fixed categorical effects, and Baseline A1C-by-time interaction as a covariate.

In addition, change from Baseline in SBP (mm Hg) at Week 16 will be summarized and analyzed using MMRM statistics with the change from Baseline at Week 16 as the endpoint and Baseline SBP -by-time interaction as a covariate, for the following subgroups:

- Baseline SBP <130 mm Hg
- Baseline SBP <140 mm Hg
- Baseline SBP ≥ 140 mm Hg

All subgroup analyses will be exploratory.

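### The primary CMH test uses A1C only as ≤9% versus >9%; it is valid and well powered, but gives up precision that continuous Baseline A1C would recover

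*SAP*

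**What the plan says.** Protocol synopsis (Statistical Methods) and Protocol 10.4.1: "Primary analysis of the primary efficacy endpoint at Week 24 will use a Cochran-Mantel-Haenszel (CMH) test stratified by BMI at Screening", Week -2 A1C (≤9%, >9%) and CSII use. SAP 6.8 repeats this for all binary endpoints. SAP 6.8.1 applies it to the primary one: "Analysis of the primary efficacy endpoint at Week 24 will be performed using the CMH test and 95% CLs", the limits being a normal approximation with a continuity correction.

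On A1C at entry, Protocol 6.1 says: "At the Screening Visit, A1C must be between 7.0% and 11.0%, inclusive". Protocol Appendix A schedules A1C again at Week -2 and Day 1.

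Finer A1C information is used elsewhere. The MMRM for A1C change (SAP 6.8 and 6.8.3.1) contains the Week -2 stratum and also continuous Baseline A1C by time. SAP 6.8.5 lists "Stratification categories of Week -2 A1C" among its subgroups and adds splits at 7.7% and 8.5%.

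The sensitivity analyses of the primary endpoint (SAP 6.8.2) change the population or the cut-off date for events, not the covariates. Protocol 10.4.1 places the confidence interval on the observed difference in proportions, and SAP 6.8 and 6.8.1 describe no stratum weighting for it.

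**The concern.** A patient who starts at 7.1% and one who starts at 8.9% are in the same A1C class, yet they are at very different distances from the 7.0% threshold that defines response. Chance imbalance in A1C within the ≤9% class therefore stays in the primary comparison as noise, although the information needed to remove it is already in the database.

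Two features give this some weight. The primary test gates every secondary hypothesis (SAP 6.8). The planned effect also rests on thin data: the sample-size section says little is known about the A1C component in this population, borrows partly from a type 2 diabetes trial, and introduces its variance assumption with "Since the underlying placebo rate is unknown for the composite outcome". If the true effect is smaller than planned, efficiency matters more.

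**Working it through.** **1. Plan figures.** Inputs from SAP 2.3 and 6.1: "90% power, 380 patients are needed per treatment group to detect a difference in binomial proportions of at least 0.12"; "the mean of the pooled responses rates is 0.50"; "All significance tests will be 2-sided and use a 0.05" level.

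n = [1.96·√(2p̄q̄) + 1.2816·√(p₁q₁+p₂q₂)]²/d², then n_cc = (n/4)·[1+√(1+4/(nd))]².
- 0.44 vs 0.56: n = 362.8, n_cc = 379.2, so 380 (matches).
- 0.45 vs 0.55: n = 523.3, n_cc = 543.1, so 544 (matches).
- Severe-hypoglycemia half-width: 1.96·√(2·0.1·0.9/700) + 1/700 = 0.0314 + 0.0014 = 0.0329 (stated 0.033).

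**2. Power at 700 per group with no A1C adjustment (0.45 vs 0.55).** Φ[(0.10·√700 − 1.96·√0.5)/√0.495] = Φ(1.79) = 96.3%. Replacing 0.10 by 0.10 − 1/700 gives 95.9%.

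**3. Assumptions for the A1C comparison.** The documents give neither a baseline A1C distribution nor its relation to Week 24, so all of these are assumed:
- Baseline A1C truncated normal on 7-11%, mean/SD 8.2/0.9, 8.2/0.7 or 8.5/1.0 (13-33% of patients above 9%).
- Week 24 A1C on baseline: slope 0.5-0.9, residual SD 0.6-0.8.
- 85% free of severe hypoglycemia and DKA (SAP 2.3).
- Response rates 0.15 vs 0.25, 0.17 vs 0.27 (17% is the registry rate for A1C <7.0% in Protocol 3.7) and 0.45 vs 0.55 (SAP 2.3).

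This makes 36 scenarios. The base case is mean/SD 8.2/0.9, slope 0.7, residual SD 0.7.

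**4. Spread inside the ≤9% class.** The response chance at baseline x is m(x) = 0.85·Φ[(7 − c − 0.7x)/0.7], and c = 1.90 gives an overall placebo rate of 0.17. At 7.1% this is 0.85·Φ(0.19) = 0.49. At 8.9% it is 0.85·Φ(−1.61) = 0.05.

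**5. Variance of the risk difference.** V = E[m₀(1−m₀) + m₁(1−m₁)], with m averaged within whatever A1C classes are used, and SE² = V/700. Base case:

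| A1C used as | V, 0.17 vs 0.27 | V, 0.45 vs 0.55 |
|---|---|---|
| not used | 0.338 | 0.495 |
| split at 9% | 0.319 | 0.444 |
| cuts at 7.7, 8.5, 9 | 0.290 | 0.416 |
| continuous | 0.285 | 0.409 |

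Continuous A1C versus the 9% split has relative efficiency 0.319/0.285 = 1.12 and 0.444/0.409 = 1.09. Over all 36 scenarios the range is 1.04-1.27, a variance reduction of roughly 4-20%. Compared with no A1C at all, the 9% split lowers variance by 2-24% and continuous A1C by 6-31%. The split keeps about 18-75% of the available gain.

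**6. Power, base case, 700 per group.**
- 0.45 vs 0.55: 97.8% (9% split) and 98.5% (continuous).
- 0.17 vs 0.27: 99.7% and 99.9%.
- 0.17 vs 0.22, half the planned effect, simulated: planned CMH 68%, CMH with the finer cuts 73%, logistic 73%.

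Across the scenarios at a difference of 0.10, the gain never exceeded about 1.3 points. A separate simulation with other assumptions (5% event failures, 12% missing) moved power from 0.962 to 0.978 at its low end, or 1.6 points.

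**7. Type I error (simulated, 1000 trials, 0.17 in both arms).** 4.9% for the planned CMH and 4.9% for the adjusted analyses.

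**8. Interval.** On the observed difference at 0.17 vs 0.27, the half-width is 1.96·√(0.338/700) + 1/700 = 0.0445 (simulated mean 0.0444). The standardised risk difference with continuous A1C gave 0.0395, about 11% narrower. Part of this is the continuity correction: without it, 0.0430 against 0.0395 is 8%.

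**The case against.** The planned test is not an error. It is stated consistently in both documents, matches the randomization, needs no outcome model and held its level in simulation. The sample size takes no credit for covariates, and 700 per group exceeds the 544 needed because precision on severe hypoglycemia was wanted. All of this stands, so the point concerns efficiency only.

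The size of the gain rests on undocumented inputs. With a weak baseline-to-Week-24 slope (0.5) the variance reduction falls to around 3-5%. That also stands, and is why a range is given.

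Replacing the CMH changes the confirmatory test named in the protocol. That is a real cost, carried into the fix.

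Finer A1C is also not ignored: the subgroup analyses use it, and so does the first secondary endpoint. True, but neither adjusts the primary estimate.

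A reader might infer more than the documents support:
- That A1C is practically unused in the primary test. The 9% split keeps somewhere between a fifth and three quarters of the gain.
- That baseline A1C is established as the dominant predictor. This is plausible from the endpoint definition, but neither document says so.
- That the loss is large because a 4-20% variance reduction equals 1400·(1/0.96 − 1) = 58 to 1400·(1/0.80 − 1) = 350 patients. The arithmetic is right, but the trial is not short of patients for this endpoint.

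**Conclusion.** The primary test uses A1C coarsely, and the loss of precision is avoidable with data already planned. Validity and planned power are not in question. Under the assumed distributions, continuous Baseline A1C lowers the variance of the risk difference by roughly 4-20% compared with the 9% split. That adds at most 1-2 power points at the planned difference of 0.10, and about 4-5 points if the true effect is half that (base case only).

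The interval is the more concrete weakness. As written, it takes no account of the strata, so it appears to lose even the 9% split and need not agree with the stratified test. This rests on the protocol's reference to the observed difference and on the SAP's silence about weights. It would fall away if stratum weighting is intended but not written down.

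**What to change.** Before unblinding, and logged in SAP section 7 as a change from the protocol:

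1. In SAP 6.8.1, fit a logistic model with treatment, continuous Baseline A1C, and the BMI, Week -2 A1C (≤9%, >9%) and CSII strata. Keeping the Week -2 stratum respects the randomization and matches the MMRM. Non-responder imputation is unchanged.
2. Name the standardised risk difference with a robust 95% CI as the single decisive test and estimate, so that test and interval agree. Keep the 8-stratum CMH as supportive.
3. If the CMH must remain primary, there are two options. Either prespecify the adjusted risk difference and its matching CI as the reported estimate or as a supportive analysis, or stratify Week -2 A1C at 7.7, 8.5 and 9. In the base case those cuts recovered most of the gain (V of 0.290 against 0.285 for continuous). They double the cells from 8 to 16, so a pooling rule for sparse cells is needed.

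Cost: SAP text and one extra program, with no new data. Options 1 and 2 also depart from the protocol-stated primary test, which gates the secondary hierarchy, and rely on a working model. If the protocol itself is amended, Protocol 11.4 requires IRB or ERC approval. Adding the adjusted analysis as supportive under option 3 avoids the change to the confirmatory test.

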6.8.2 Sensitivity Analysis

Analysis of the primary efficacy endpoint, as described in [Section 6.8.1](#), will also be performed on the PP population as a sensitivity analysis.

Statistical Analysis Plan

Version: Final 1.0

Lexicon Pharmaceuticals Protocol No. LX 4211.1-312-T1DM

Date of Issue: 17 MAR 2017

Covance Study ID: 000000145143

Sensitivity analysis of the primary efficacy endpoint will be performed by applying the patient's date of the last dose of double-blind study drug as the cut-off for inclusion of SH and DKA events in the analysis.

Another analysis will be performed by applying 30 days after the patient's date of the last dose of double-blind study drug as the cut-off for inclusion of SH and DKA events in the analysis.

6.8.3 Secondary Efficacy Analysis

Analysis of the secondary efficacy endpoints will be based on the mITT population. Descriptive statistics for secondary efficacy endpoints will be presented by treatment group and by study visit where appropriate. All post-Baseline data will be used in the analyses where inferential statistics are presented, including observations occurring after discontinuation of study drug. The secondary efficacy endpoints are to be measured as change from Baseline in LX4211 400 mg compared to placebo for each of the following sections and will be analyzed using MMRM model as specified for continuous efficacy endpoints in [Section 6.8](#).

Figures displaying mean change from Baseline by visit and LS mean change at Week 24 will be presented by treatment groups.

6.8.3.1 Change from Baseline in A1C at Week 24

Descriptive statistics of A1C at each visit, the change from Screening to Baseline in A1C, and the change from Baseline in A1C at post-Baseline visits will be presented by treatment group and visit. The treatment effects at Week 24 will be evaluated using MMRM statistics with the change from Baseline as the endpoint and Baseline A1C -by-time interaction as a covariate.

